### 7.3 Follow-up Participant Assessments

The event that starts the post-intervention data collection timing are as follows.

Acute Pain:

- Date of surgery (intervention and control arms)

Chronic Pain and Depression:

- Intervention arm: When the pharmacogenetics results are returned to the provider and deposited in the EMR
- Control arm: At date of DNA sample collection plus one week, where one week reflects the average time from sample collection to returning the results to the EHR
- Note: There will be variability in time the results are returned to provider and when genotype-guided therapy is delivered to the participant, time from results being available to the next provider-participant interaction (e.g. email, clinic visit, new prescription order, phone visit, etc.) will be recorded by study personnel.

Post intervention assessment collection may be done by the University of Florida College of PharmacyCall Center. The center agents will be trained survey collectors\*, using an IRB approved telephone script. The collected survey responses will be entered into the study database. If preferred, the participant will have the option to complete the study follow-up survey by a URL link sent by text (to mobile phone) or email and captured in REDCap database

In the event that the call center is unable to reach a participant, local study coordinators may contact participants to facilitate completion of the follow-up surveys.

Data will be collected in the following timeframes\*:

- Acute pain: 10 days, 1 month, 3 months, and 6 months post-surgery
- Chronic pain and depression: 1-month, 3 months, and 6 months post return of results for the intervention arm, and post baseline assessments for the control arm.

\*See *MOP for call center agents and survey collection interval windows*

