### 3. ENDPOINTS

#### 3.1 Primary Endpoint(s)

**Acute pain:** The primary endpoint for the acute pain study is the SIA score, a composite of pain and opioid usage, at 10 days post-surgical procedure. See Appendix A for the SIA score rationale.

**Chronic pain:** The primary endpoint for the chronic pain study is change in composite pain intensity score, assessed using the PROMIS pain intensity survey, from baseline to 3 months post return of genetic testing results to the provider.

**Depression:** The primary endpoint for the depression study is change in depression score, assessed using the PROMIS Emotional Distress - Depression 8b survey (adults) or PROMIS pediatric depressive symptoms (pediatric), from baseline to 3 months post return of genetic testing results to provider.

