## 7.2 Baseline Participant Assessments

All study participants will complete baseline surveys for demographics and participant reported outcomes (PROs) (see Table 8 for details). These data will be collected by the study coordinator in person or alternatively by using telephone, email, or text.

Baseline data will be collected for the Chronic Pain and Depression trials following consent, for the Acute pain trial, survey data will be collected before surgery. The type of surgery information will be collected after the completed procedure.

*Participant demographics* – including but not limited to age, sex, gender, race, Hispanic/Latino ethnicity (Yes or no), and smoking status will be administered at baseline as a survey.

*Past medical history* – A snapshot of the participant's medical history. See MOP for details.

*Baseline medications* - Participant medications will be collected through the EHR and/or participant self-report. See MOP for details.

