**Chronic Pain:**

**PROMIS pain intensity scale** – A participant completed 3-question survey of average pain over the last 7 days, worst pain over the last 7 days, and current pain. Each question is on a 1-5 integer scale, the

higher the value, the more intense the pain. This survey will be administered at baseline, 1 month, 3 months, and 6 months post return of results.

*PROMIS prescription pain medication mis-use scale* - A participant completed survey of prescription medication misuse over the past 30 days. The survey is comprised of 7 questions on a 5-point ordinal scale of never/rarely/sometimes/frequently/almost always or not at all/a little bit/somewhat/quite a bit/very much[33]. This survey will be administered at baseline, 3 months, and 6 months post return of results.

*PROMIS emotional distress depression 8b survey* - A participant completed eight question survey assessing frequency of depression symptoms over the past 7 days[36]. This survey will be administered at baseline, 1 month, 3 months, and 6 months post return of results to the adult participants.

*Opioid side effects* – A participant completed survey of common opioid side effects experienced and the extent to which those side effects bothered the participant. This survey will be administered at baseline, 3 months, and 6 months post return of results to the adult participants.

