#### **Depression:**

*PROMIS emotional distress depression 8b survey* - A participant completed eight question survey assessing frequency of depression symptoms over the past 7 days[36]. This survey will be administered at baseline, 1 month, 3 months, and 6 months post return of results to the adult participants.

*PROMIS Pediatric Depressive Symptoms Short Form 8a*- A pediatric (ages 8-17 years) participant completed eight question survey assessing frequency of depression symptoms over the past 7 days[37]. This survey will be administered at baseline, 3 months, and 6 months post return of results to the pediatric study participants .

*Patient Health Questionnaire-8* – An 8 item survey completed by the participant assessing depression symptoms over the last two weeks. This survey will be administered at baseline, 3 months, and 6 months post return of results[38].

*Antidepressant side effects* – A participant completed survey of relevant antidepressant side effects. This survey will be administered at baseline, 1 month, 3 months, and 6 months post return of results.

*Voils Medication Adherence* - A participant completed three question survey, 5-point scale survey assessing participant medication adherence[39]. This survey will be administered to depression trial participants at baseline, 1 month, 3-months and 6 months post return of results.

All of the PROMIS® surveys can be found online[40].

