## 7.5 Specimen Transfer and Genetic Testing Procedures

All collected specimens will be clearly marked with two patient identifiers (CLIA requirement). Samples from the Intervention arm participants will be processed, using analytically validated PGx testing procedures (see Table 1 for gene and variant list). For Control arm samples, designated laboratories will either extract DNA after sample receipt, and store the DNA for later analysis or store the sample and extract DNA after the Control participant has completed the 6-month follow-up assessment. After the Control participant has completed the 6-month follow-up assessment, Control Arm samples will be processed using analytically validated procedures. Details of sample storage and transport will be presented in the MOP.

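### Section 7.3 gives control participants in the chronic pain and depression trials two different time zeros; using the baseline one would shift the 3-month survey by arm (by 7 days if survey and sample fall on the same day)

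*Combined protocol and SAP*

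**What the plan says.** Section 7.3 opens its timing rules with "The event that starts the post-intervention data collection timing are as follows". For chronic pain and depression, the intervention arm starts when results reach the provider and the medical record. For controls the rule is "Control arm: At date of DNA sample collection plus one week, where one week reflects the average time" from sample to results in the record. This is a stand-in date, chosen to mirror the intervention arm.

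Lower in the same section, the list of timeframes places the 1-, 3- and 6-month surveys "post return of results for the intervention arm, and post baseline assessments for the control arm". That is a different anchor for controls.

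Other sections do not settle the matter:

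- Section 3.1 defines the chronic pain primary endpoint as change "from baseline to 3 months post return of genetic testing results to the provider", with matching wording for depression. Neither separates the arms.
- The primary instruments are described the same way: "This survey will be administered at baseline, 1 month, 3 months, and 6 months post return of results" for pain intensity and "This survey will be administered at baseline, 1 month, 3 months, and 6 months post return of results to the adult participants" for adult depression.
- Controls have no results date during follow-up. Section 7.5 says "After the Control participant has completed the 6-month follow-up assessment, Control Arm samples will be processed".
- On baseline, section 7.2 says "Baseline data will be collected for the Chronic Pain and Depression trials following consent". Section 7.4 also places DNA sampling after consent, allows mailed kits, and puts sampling before randomization. The order of survey and sample, and the gap between them, are not fixed.
- Table 8 allows 14 days either side of the 3-month visit.
- The primary tests in section 10.4 compare change from baseline between arms and include no term for elapsed time.

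**The concern.** The primary endpoint in both trials is change from baseline to 3 months. If the two arms are surveyed at different mean times since baseline, improvement that would have happened anyway during the extra days counts as treatment effect. A two-sample test on the change score cannot separate the two.

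Continuing improvement is plausible in depression, because section 5.1 requires recently started, recently revised, or anticipated new or revised SSRI therapy. In chronic pain the documents support neither a direction nor a size. There is also a practical risk: sites or call-center staff working from different sentences of section 7.3 could apply different rules.

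**Working it through.** **Inputs from the documents.** Intervention time zero = sample date + turnaround T. Control time zero = sample date + 7 days (sample rule) or the baseline assessment (baseline rule). Average turnaround is stated as one week (all 7.3). For depression: SD 10, planned difference 2.8 T-score points, 271 per arm, alpha 0.049 (10.1).

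**Notation.** L = mean of (sample date minus baseline survey date): positive if the survey comes first, negative if the sample does. Three months = 91 days.

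**The plan's own figures.** The one-week turnaround is stated without data, so it cannot be reproduced. The sample sizes can: a two-sided t-test at alpha 0.049 and 90% power gives 133.02, rounded up to 134 per arm at effect size 0.40 (chronic pain), and 270.45, rounded up to 271 at 0.28 (depression). Both agree with Table 9, and neither depends on time zero.

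**Mean days from baseline survey to 3-month survey**

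- Intervention: L + T + 91
- Control, sample rule: L + 7 + 91
- Control, baseline rule: 91

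If mean L is the same in both arms, intervention minus control is T - 7 under the sample rule and T + L under the baseline rule. At T = 7:

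| L (days) | Intervention | Control, sample rule | Control, baseline rule | Gap, sample rule | Gap, baseline rule |
|---|---|---|---|---|---|
| -14 | 84 | 84 | 91 | 0 | -7 |
| -7 | 91 | 91 | 91 | 0 | 0 |
| -3 | 95 | 95 | 91 | 0 | 4 |
| 0 | 98 | 98 | 91 | 0 | 7 |
| +7 | 105 | 105 | 91 | 0 | 14 |

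The baseline rule matches the arms only if the survey follows the sample by 7 days on average.

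**Two conditions on the sample rule.** If mean turnaround is not 7 days, it is off by T - 7: -2 days at T = 5, +3 at 10, +7 at 14, +14 at 21. If mean L differs between arms, that difference adds directly: 3 days' difference in L gives a 3-day gap.

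**Illustrative size in depression.** The documents give no drift rate. Assume both arms improve by 0.5 to 1.5 T-score points a month near month 3, and take L = 0 and T = 7 under the baseline rule:

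- Bias = rate x 7 / 30.4 = 0.115 to 0.345 points.
- Share of the planned effect: 0.115 / 2.8 = 4.1%; 0.345 / 2.8 = 12.3%.
- Standard error = 10 x sqrt(2 / 271) = 0.859.
- Rejection rate with no true effect (noncentral t, 540 df, two-sided alpha 0.049): 5.1% to 6.7%, against a nominal 4.9%.

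At L = -7, or if scores have levelled off by month 3, the added bias is zero.

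**The case against.** The strongest reply is that this is leftover wording and not a second operating rule. Sample plus one week appears under the sentence that defines what starts the clock, and it carries its own justification. The other statement is a clause in a summary bullet, whose heading refers the reader to the manual of operations for survey windows. Figure 1, section 7.8 and Table 8 use a time-zero concept. The amendment log records that section 7.8 was corrected from baseline to time-zero, which suggests that the sponsor had used the two terms loosely. On this view, the generic return-of-results wording in 3.1 and the instrument list is shorthand. Much of this stands: the sample rule does read as governing. But the conflicting clause is in the current text, and nothing visible withdraws it.

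A second reply is that a 7-day shift lies inside the 14-day window of Table 8. True, but the window limits scatter around each visit. It does not remove a shift that affects one arm only.

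A third is that the size in points rests wholly on an assumed drift rate. That also stands, and the figures are illustrative only.

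On the other side, a reader might infer that the sample rule matches the arms whatever the order of survey and sample. The documents do not guarantee this. It requires the same mean L in both arms. Sampling precedes randomization, but no current section requires the baseline survey to do so. A survey taken after the sample could therefore follow open-label allocation, and L could differ by arm. Nor can the sample rule's residual error be called small, because no observed turnaround or range is given.

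**Conclusion.** Section 7.3 contains two incompatible control time zeros for the chronic pain and depression trials, and this should be fixed. The sample rule reads as governing. It matches the arms on mean time since baseline if mean turnaround is 7 days and mean L is equal between arms. The baseline rule would survey controls 7 + L days earlier, a shift that is systematic by arm and that the primary test does not address.

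For depression, with survey and sample on the same day and the assumed drift, the effect is modest: 0.12 to 0.35 points and a false-positive rate of 5.1% to 6.7%. For chronic pain, no size or direction is supported.

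A reader might infer that controls were in fact surveyed early and that the primary comparisons are biased. The documents do not show this. Figure 1, the manual of operations and the separate trial analysis plans are not available here, so neither the rule used nor any handling of elapsed time elsewhere can be seen. Confidence is high in the textual conflict and the day arithmetic only.

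**What to change.** 1. Check the manual of operations, Figure 1 and conduct to date to establish which control rule was applied.
2. Reconcile section 7.3 to one control time zero. Sample collection plus one week is the rule the protocol itself justifies, so delete the control-arm clause that ends "post return of results for the intervention arm, and post baseline assessments for the control arm". Document any participants surveyed under the other rule.
3. In section 3.1 and the instrument descriptions in 7.3, define 3 months by the arm-specific time zero.
4. Compare the one-week offset with the observed mean turnaround. Report by arm the days from baseline survey to 3-month survey, and L.
5. Leave the primary test unchanged. Optionally, prespecify one sensitivity analysis per trial, for example the repeated-measures mixed model already planned in section 10.6, with actual days since the baseline survey as the time scale and the arm difference estimated at a common day.

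The cost is a document check, a few wording changes and one table per trial, provided survey and sample dates are in the database. The optional model depends on the time shape it assumes. In depression it also has fewer time points for children, because section 7.3 schedules no 1-month assessment for the pediatric depression form. It should therefore support the primary test and not replace it.

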#### All Trials

*PROMIS 43* – Adults ( $\geq 18$  years of age) will complete a 43-question survey assessing well-being and sub domains: pain interference, physical function, sleep disturbance, social role and activities functioning, fatigue, anxiety, and depression.[32] This survey will be administered to adult participants at baseline, 1-month, 3-months, and 6-months post-surgery (acute pain), or baseline, 1-month, 3-months, and 6-months post return of results (chronic pain, depression).

*PROMIS pediatrics 37* – Pediatric study participants (ages 8-17) will complete a 37-question survey assessing pediatric well-being and sub domains: pain interference, physical function, sleep disturbance, social role and activities functioning, fatigue, anxiety, and depression. This survey will be administered to pediatric participants at baseline, 1-month, 3-months, and 6-months post-surgery (acute pain), or baseline, 1 month, 3 months, and 6 months post return of results (depression).

*Health care utilization* – Survey of the number of significant cost driver health care encounters (e.g. hospitalizations, clinic visits, etc.). This survey will be administered to participants at 10-day, 1-month, 3-months, and 6-months post-surgery (acute pain), or baseline, 1-month, 3-months, and 6-months post return of results (chronic pain, depression).

**Medications** - Participant medications will be collected using patient surveys at baseline and the primary endpoint time points: 10-days for Acute Pain and 3-months for Depression and Chronic pain.

**Productivity loss** – Survey of loss of work the time and pay lost due to the participant's depression or pain. This survey will be administered to participants at 1-month, 3-months, and 6-months post-surgery (acute pain), or 1-month, 3-months, and 6-months post return of results (chronic pain, depression).

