## 7.9 Data Collection from CMS and State Medicaid Agencies

Medicare and Medicaid claims data from CMS and state Medicaid agencies will be used to assess health care utilization, costs, and medications among participants covered by either Medicare or Medicaid. Claims made in the period of 12 months prior to surgery (acute pain) or return of results (chronic pain, depression) through 6 months following those events will be collected. See Section 9 and the MOP for additional details. Schedule of Activities and Timeframe for Collection of Endpoints

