**Table 8. Data collection schedule**

### Data collection schedule, method of data collection, and timing

Outcome	Data source/instrument	Baseline	10 d ± 3 d	1 mo. ± 7 d	3 mo. ± 14 d	6 mo. ± 14 d
Pain Assessments						
Pain intensity	PROMIS Pain intensity scales	AP, CP	AP	AP, CP	AP, CP*	AP, CP
Pain intensity	PROMIS Numeric Rating Scale - Pain Intensity (NPRS)	AP	AP*	AP	AP	AP
Daily opioid dose & type of opioid use	Average daily mg morphine equivalents (MED) since discharge use of opioids: tramadol/ codeine vs others		AP*	AP		
Opioid use disorder	PROMIS - Prescription pain medication misuse subscale	AP, CP			AP, CP	AP, CP
Mobility	PROMIS mobility	AP	AP	AP	AP	AP
Depression Assessments						
Depressive state	PROMIS Emotional Distress - Depression 8b survey	CP, D		CP, D	CP, D*	CP, D
Depressive state	Patient Health Questionnaire-8 depression scale	D			D	D
Participant Medications						
Assessment of prescriptions	Custom survey/EHR	AP, CP, D	AP		CP, D	
Assessment of filled prescriptions	Medicaid and Medicare billing records for 12 months prior to time 0 through 6 months after time 0		AP, CP, D			

Adherence	Voils Medication Adherence		D		D	D	D
SSRI AE Survey	Custom survey		D		D	D	D
Opioid side effect survey	Adapted medication side effect survey (SPACE)		AP, CP	AP	AP, CP	AP, CP	AP, CP
Opioid persistence	Custom survey						AP
Participant Actions							
Interaction with provider	Participant visits				CP, D		
Interaction with test result	Custom survey						AP, CP, D
Quality of life and well being							
Past Medical History	Participant visits/custom survey		AP, CP, D				
Well-being	PROMIS43/PROMIS Peds37		AP, CP, D		AP, CP, D	AP, CP, D	AP, CP, D
Healthcare Utilization and Costs							
Medicare/Medicaid billing records	Medicaid and Medicare billing records for 12 months prior to time 0 through 6 months after time 0				AP, CP, D		
LoS	LoS for index admission			AP			
ED/urgent care & inpatient visits	Participant reported visits				AP, CP, D	AP, CP, D	AP, CP, D
Outpatient visits	Participant reported primary care & pain clinic visits				AP, CP, D	AP, CP, D	AP, CP, D
Outpatient visits	Long-term care or in-patient rehab days, home healthcare days				AP	AP	AP
Productively Loss	Survey of lost work time and income				AP, CP, D	AP, CP, D	AP, CP, D

Abbreviations: CP – chronic pain, AP – acute post-surgical pain, D-depression, ED – emergency department, EHR – electronic health record; LoS – length of stay; PT – physical therapy

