### **8.2 Events of Interest**

Participant reported emergency department visits and hospitalizations will be collected in the 1, 3, and 6-month follow-up participant surveys. EHR may be used as an additional source for emergency department visits and hospitalizations, up to approximately 12 months after the last patient is randomized, i.e. through completion of the 6 month-follow up activities. For the details of collecting EHR data, see Protocol section 7.8 and MOP. EHR results will be sent to the CC via secure data transfer and formatted for data analyses.

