### 9.2 Data Collection

Data for this specialized analysis will come from these sources:

1. Participant report of healthcare utilization (e.g. emergency department, urgent care, office) for all participants, these will focus on high-cost items and/or items that are expected to be sensitive to the intervention
2. Medicare claims data for Medicare enrollees
3. Medicaid claims data for Medicaid enrollees

*Participant reported visits:* Participant reported assessment for health care utilization is previously described in section 7.3.

*Medicare claims data:* For Medicare enrollees in fee-for-service (FFS) plans or Medicare Advantage, clinical groups will ascertain Medicare claims data (Part A-D) directly from the Centers for Medicare and Medicaid Services (CMS).

*Medicaid claims data:* For Medicaid enrollees, clinical groups will ascertain claims data from their states' Medicaid agencies directly.

To ensure full adjudication, requests to Medicare/Medicaid for claims data will be timed to occur between 6-12 months after the end of the 6-months follow-up of the last enrolled patient. Claims data will also be requested for one year before trial enrollment up to 6 months thereafter.

The procedure for obtaining claims data will require a database linkage step – mapping the participant study ID to the Medicare/Medicaid identifiers. The data linkage will rely on social security number (SSN) or Medicare ID and date of birth (DoB), which can be collected in two possible ways:

1. Both SSN and/or Medicare ID and DoB are collected as part of the trial by the recruiting site
2. One or both variables are extracted from the medical record of the participating health center by a healthcare data security officer or the local equivalent, on behalf of the study team

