#### Cost Effectiveness

*Healthcare costs:* In the Medicare fee-for-service or Medicaid enrollees, log-transformed overall expenditures (between index visit and 6 months follow-up) will be compared using a 2-sample t-test between the study arms (after ensuring that the variances in the log-scale are equal). Alternatively, cost comparisons will be made using appropriate regression models such as generalized linear models. For all participants, regardless of insurance type, we will estimate and aggregate participant-reported healthcare utilization during follow-up and assign cost for each item based on unit weighted mean cost estimates from the Medicare/ Medicaid data.

Within the Medicare/Medicaid population, we will compare estimated cost differences between genotype-guided and usual care based on billing records versus participant report to further validate the cost comparisons for the entire population. Cost for the index hospitalization for surgery participants will not be included in the cost estimate, but we will compare length of stay between groups as reference for hospitals regarding potential cost savings in capitation-based reimbursement schemes. All costs will be converted to 2021 \$US using the chain-weighted Consumer Price Index (CPI).

Finally, we will compare the Medicare/Medicaid beneficiaries among our trial enrollees to a larger random sample of beneficiaries in the participating states and compare demographic and key clinical characteristics to explore representativeness of our study sample, evaluate the impact of attrition and loss to follow-up and make inferences about the generalizability of our results.

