*Cost utility:* For the cost-utility analysis, the PROMIS-43 responses will be converted into utilities using previously validated crosswalks.[41] Cost and quality adjusted life year (QALY) estimates, adjusted for clustering within site and baseline utility for QALYs, will be obtained using appropriate regression models such as generalized linear models. The analysis of maximum likelihood parameter estimates will allow us to capture differences in cost and QALYs between the intervention arm and control arm of the trial. The Incremental cost-effectiveness ratio (ICER) will be calculated from costs and QALY. A bootstrapping approach will be used to characterize sampling uncertainty and calculate confidence intervals (CI) around the ICER estimate (2.5th and 97.5th percentiles corresponding to the lower and upper bounds of the CI, respectively). This sampling uncertainty will be summarized using cost-effectiveness acceptability curves.

Details of these statistical analyses, along with other exploratory analyses will be described in the study SAP.

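### A year of pre-index claims is obtained, but no cost analysis names prior cost as a covariate, and section 7.3 and Table 8 disagree on the baseline utilization survey

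*Combined protocol and SAP*

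**What the plan says.** **Claims.** Section 7.9 covers "Claims made in the period of 12 months prior to surgery (acute pain) or return of results (chronic pain, depression) through 6 months" after those events, and Table 8 repeats the 12 months before time 0. Section 9.2 uses a different anchor: "Claims data will also be requested for one year before trial enrollment up to 6 months thereafter".

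**Utilization survey.** Section 7.3 (All Trials, Health care utilization) has it "administered to participants at 10-day, 1-month, 3-months, and 6-months post-surgery (acute pain), or baseline, 1-month, 3-months, and 6-months post return of results" in chronic pain and depression. So those two trials have a baseline administration and acute pain does not. In Table 8 the self-reported visit rows, such as "Participant reported primary care & pain clinic visits", are marked at 1, 3 and 6 months only. Section 7.2 points the reader to Table 8 for the baseline surveys.

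**Cost analysis.** Section 10.6 (Cost Effectiveness, Healthcare costs) restricts its first test to people in Medicaid or fee-for-service Medicare and reads: "log-transformed overall expenditures (between index visit and 6 months follow-up) will be compared using a 2-sample t-test between the study arms". It then allows regression models, such as a GLM, as an alternative and lists no covariates for them. Under Cost utility, the cost and QALY estimates are "adjusted for clustering within site and baseline utility for QALYs". Further detail is deferred to a separate SAP.

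**The concern.** Health care costs are skewed and vary widely between people, so a comparison of arms on follow-up cost alone is noisy. A baseline value of the same quantity is the usual way to reduce that noise, and here it will already be in hand for claims participants. The plan adjusts the effect side of the cost-effectiveness ratio for baseline utility but names nothing equivalent for the cost side.

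For clinical endpoints, section 10.6 itself recognises that baseline characteristics may differ between the compared groups and plans covariate-adjusted models. Chance differences can equally arise in the subset with claims.

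The schedule conflict adds a practical loss. A site that follows section 7.2 to Table 8 collects no baseline utilization. For participants without claims there is then no other stated source, because the EHR encounter data in section 7.8 begin at time zero. Section 9.1 expects claims for at least 60%, so this could affect up to about 40%.

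**Working it through.** **1. Where pre-index utilization is collected**

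| Place | Chronic pain, depression | Acute pain |
|---|---|---|
| 7.3 survey | baseline, 1, 3, 6 months | 10 days, 1, 3, 6 months |
| Table 8 visit rows | 1, 3, 6 months | 1, 3, 6 months (length of stay only at 10 days) |
| 7.8 EHR encounters | from time zero | from time zero |
| 7.9 claims | 12 months before return of results | 12 months before surgery |
| 9.2 claims | one year before enrollment | one year before enrollment |

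Section 7.3 and Table 8 conflict on baseline in chronic pain and depression, and on the 10-day visit survey in acute pain. Sections 7.9 and 9.2 conflict on the claims anchor.

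**2. What each cost analysis adjusts for**

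- t-test on log cost: nothing.
- Regression or GLM alternative: covariates not named.
- Cost-utility models: site clustering for both outcomes, baseline utility for QALYs, no baseline term for cost.
- Cost imputation (section 9.2): claims and self-report, no pre-index term named.

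**3. Size of the precision loss**

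The plan gives no SD, effect size or sample size for the cost comparison, so there is no figure to reproduce. It also gives no correlation r between pre-index and follow-up cost; the values below are assumptions. For a linear model on the log scale, baseline adjustment multiplies the variance of the arm difference by 1 − r².

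- r = 0.3: 1 − 0.09 = 0.91, a 9% cut; 1/0.91 = 1.10 times the sample.
- r = 0.5: 1 − 0.25 = 0.75, a 25% cut; 1/0.75 = 1.33 times the sample.
- r = 0.6: 1 − 0.36 = 0.64, a 36% cut; 1/0.64 = 1.56 times the sample.

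Standard errors, and so interval widths, shrink by √(1 − r²) = 0.954, 0.866 and 0.800. For a GLM these are approximations.

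**4. Illustration in chronic pain**

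Inputs: 994 randomized (section 10.1), 1:1 allocation (4.1), 60% with claims (9.1), two-sided 0.05 (10.2). The 80% power is an assumption, and drop-out is ignored.

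- Per arm with claims: 0.60 × 994/2 = 298.2.
- Minimum detectable difference, unadjusted: (1.960 + 0.842) × √(2/298.2) = 0.229 SD of log cost.
- Adjusted, multiplying by the factors in step 3: 0.219, 0.199 and 0.184 SD at r = 0.3, 0.5 and 0.6.

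**5. Whether the collected window can serve as the covariate**

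Section 7.4 places randomization after sample collection. In chronic pain and depression, section 7.3 sets time 0 at the actual return of results in the intervention arm and at the sample date plus one week in the control arm. If randomization falls on the sample day, about 7/365 = 2% of a control participant's 12-month pre-time-0 window lies after randomization. In the intervention arm that share depends on how long the result takes. The amount is small on average, but a covariate should be fixed before allocation and defined identically in both arms. In acute pain the gap can be larger: section 6.3 makes surgery not taking place within 12 months of enrollment a ground for withdrawal, so the two anchors can be many months apart.

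**The case against.** The best defence has four parts.

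First, section 10.6 leaves the regression covariates open and defers detail to the SAP, and the synopsis lists covariate adjustment among additional analyses. This stands in part. A reader might infer that no cost analysis will use pre-index data; the documents show only that none names it. The first-named test is still unadjusted.

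Second, under 1:1 randomization the unadjusted comparison is unbiased and its interval already allows for chance imbalance. This stands in full. A reader might infer that the cost result would be biased, or might add imbalance to the wider interval as a second harm. Neither follows.

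Third, the schedule evidence is limited. Section 8.2 says "Participant reported emergency department visits and hospitalizations will be collected in the 1, 3, and 6-month follow-up participant surveys", and a reader might take that as a second place where the baseline survey was dropped. But 8.2 deals with follow-up events and has no reason to list a baseline survey. The single mention of baseline in 7.3 could itself be a drafting slip, so the documents support reconciling the two places, not a choice between them. Nothing is lost at baseline in acute pain, since 7.3 has no baseline survey there.

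Fourth, these are exploratory analyses and the pre-index claims may also serve the planned comparison of representativeness. That limits the importance of the point but does not make the covariate less available.

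**Conclusion.** The point holds in limited form and is minor. A year of pre-index claims is obtained and no cost analysis names it; the survey schedule in section 7.3 conflicts with Table 8. The consequence is lost precision and lost protection against chance imbalance in an exploratory comparison. No primary or secondary endpoint is affected.

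The size rests wholly on an assumed correlation: a variance cut of 9% to 36% for r from 0.3 to 0.6. It is tempting to call prior cost the strongest covariate, but the documents contain nothing that ranks it. It is also tempting to compute a large chance imbalance within the actionable-phenotype subgroup. That would need an assumed cost SD, and section 10.6 compares enrollees between arms without restricting the cost analysis to that subgroup.

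**What to change.** 1. In section 10.6 and the SAP, before claims are received, make the main cost comparison among claims participants a regression or GLM adjusted for pre-index claims cost, and use the adjusted cost difference in the ICER.
2. Define the covariate window to close at or before randomization, identically in both arms.
3. Align the claims anchors in sections 7.9 and 9.2, so that the request covers both the pre-randomization year and the six months after time 0.
4. Reconcile section 7.3 with Table 8 on the baseline survey, and on the 10-day acute pain survey. Where baseline self-report was collected, use it as a separate covariate in the self-report cost analysis. Do not pool it with 12-month claims cost, since the two measure different things and 7.3 states no recall period.
5. State that acute pain participants without claims have no baseline utilization under 7.3 and stay unadjusted. Section 8.2 needs no change.

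The cost is a few sentences and no new participants. Section 9.2 times the claims request 6 to 12 months after the last participant's follow-up ends, so the covariate can be fixed before those data are seen. A baseline survey that was not given cannot be recovered for participants already enrolled.
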